3.1 Primary Endpoint

To test if CVL-562 has dose-related effects in schizophrenia patients on putative neural biomarkers of D1R/D5R stimulation. We will examine the dose-specific effects of CVL-562 on blood oxygen level dependent (BOLD) signal change during working memory procedures. The primary outcome measure is an analysis of variance of the dose-dependent effects of CVL-562 on the blood oxygen level dependent signal (BOLD) during spatial working memory. Post-hoc univariate tests will quantify directional dose-related CVL-562 effects.

3.2 Secondary Endpoint 1

To test in how many participants CVL-562 produces a dose-related modulation of BOLD signal during working memory procedures.

3.3 Secondary Endpoint 2

To test if CVL-562 produces a dose-related modulation of sWM behavioral performance collected during fMRI. This will be examined using the behavioral data generated during neuroimaging to quantify dose-related CVL-562 effects on sWM performance both with and without distractors.

3.4 Secondary Endpoint 3

We plan to directly examine the association between trial-by-trial sWM performance and task-evoked BOLD signal by regressing trial-by-trial sWM performance with and without distractors with the relevant BOLD signal.

3.5 Secondary Endpoint 4

We will examine the dose-dependent effects of CVL-562 on the functional connectivity of brain regions during spatial working memory.

3.6 Secondary Endpoint 5

We will examine the dose-dependent effects of CVL-562 on the resting state functional connectivity using a data-driven global brain connectivity (GBC) metric.

3.7 Secondary Endpoint 6

We will compare the change in resting state GBC as a function of CVL-562 dose with the transcriptomic maps from the Allen Human Brain Atlas relevant to risk genes in schizophrenia.

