advised NOT to drive to and from the testing sessions, and instead we will arrange alternative means of transportation for all subjects (e.g. taxi). A physician investigator (MD) will approve the discharge of subjects following the completion of each treatment visit. Following discharge from each treatment visit, subjects will be provided a number to call to reach an on-call psychiatrist (24 hours/day) should delayed unpleasant effects occur. Subjects who experience any intolerable effects at any point will not be permitted to continue participation. Please see Section 9.4 for further details on criteria for stopping participation. Post-testing: Contact with participants will be maintained during the study and following its completion. We will contact all subjects approximately 24 hours after drug administration to check for side effects. A final, in-person follow-up visit will occur after the last treatment visit to assess side effects and complete final bloodwork. Furthermore, we will conduct a follow-up call approximately 1 month after study completion (i.e., after the final in-person visit) to assess for late or ongoing adverse effects. Any subjects that experience lingering side effects will be followed by the study team until resolved or stabilized, and then will be directed to follow-up with their primary health care provider. All imaging will occur at sites specifically designed, equipped, and functioning in support of these types of studies, and includes the onsite presence of medical supervision with experienced medical, nursing, research and/or technical staff. Although we do not expect significant problems to occur, if any adverse effects occur during the fMRI session, appropriate treatment will be instituted for symptomatic relief. All sites will implement clear protocols for addressing medical urgencies and emergencies, including, but not limited to, emergent assessment, use of a crash cart, and transportation to the emergency room.

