4.2.1 Clinical Protocol Schedule of Events Completed by an Individual

• Pre-screening - Potential participants will be contacted by phone by a research staff member to determine whether a participant is eligible to participate in an in-person screening visit (baseline visit). The data indicating that a participant is found to be eligible for Visit 1 will be entered directly into a REDCap database. Those who fail to meet eligibility criteria on the phone screen will not be invited to the in-person screening/baseline visit and will not participate in any additional research procedures. Potential participants will then be invited for the baseline visit (in-person assessment) with a doctoral-level clinician or an appropriately trained senior research assistant. Given the longitudinal

nature of the study, as well as planning for attrition, we aim to recruit a total of 120 participants who would be eligible to receive CVL-562 based on medical and psychiatric assessments. Of those, we aim to have 100 participants complete full procedures (we have estimated attrition of 20 participants). The number of participants who are consented may exceed 120 subjects as we anticipate that some will be found ineligible on the first baseline visit due to medical or psychiatric or other reasons.

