5.2 Rescue Medication and Supportive Care

There is no rescue medication that reverses the effects of CVL-562. Intravenous or sublingual ondansetron will be available to treat acute nausea/vomiting that may occur on test days after the administration of CVL-562. For acute anxiety related to procedures in the scanner, participants will be removed from the scanner and assessed for continuation in the study.

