- Lifestyle Questionnaire—this is a structured interview to assess events that occur on the day of scanning prior to the fMRI scan being obtained. This covers information such as caffeine use, food intake and hydration. The source data is electronic and this information will be entered directly into REDCap.

7.2.2 Functional magnetic resonance imaging (fMRI).

It is important to note that research has not found any adverse side-effects of MR imaging at field strengths used in the present protocol. fMRI scans will be gathered according to the United States Food and Drug Administration (FDA) guidelines for magnet strength and exposure to radio waves. Subjects will be monitored closely throughout the scan. Some subjects feel uncomfortable or anxious and on rare occasions, subjects experience upset stomach, have a metallic taste or feel tingling sensations or muscle twitches. There are some risks with an MRI scan for certain people, if subjects have a pacemaker or some metal object inside their body for example, however, we will take exceptional precautions through an extensive MR safety screen to exclude subjects with any contraindications during initial screening (MRI safety assessment—site specific). Furthermore, we will exclude any individuals who express concern about small spaces/claustrophobia during screening. For those subjects participating in the study we will offer the optional opportunity to undergo an adaptation session in a mock scanner to provide subjects an opportunity to be familiar with lying in the MRI scanner. If a participant becomes anxious during scanning, we will initially try to relax them by speaking to them over the intercom. In our experience, participants are the most uncomfortable when first entering the magnet, and the feelings dissipate as people adapt to the situation. If the discomfort persists, or if at any time a participant requests so, we will stop the imaging session immediately. Further continuation of this participant in the remainder of the study will be determined by the study investigators in collaboration with the participant.

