As this is a multi-site neuroimaging project, we will validate neuroimaging data acquisition, transfer and processing prior to clinical data collection. These will be tested using members of the research team who will undergo neuroimaging procedures at each site. Scanning the same persons at each site will allow the research team to compare the image acquisition, as well as the collection of behavioral and eye-tracking data, at each site. We have opted for this instead of the exclusive use of phantoms, as task-based images would not be possible to collect with phantoms. Furthermore, we have opted to use research personnel who travel to each site, rather than examining the first few patients recruited, as we would like to examine image acquisition within-subject, and fully compare sites. Use of our recruited patients would not allow for within-subject comparisons of sites as the clinical protocol is meant to be carried out at one site. Ongoing stability of MRI scanners will be checked using regular phantom scanning.

[figure not shown]

Figure 2. Power Calculation for the Primary Endpoint.

Power: The Primary Endpoint is concerned with within-subject repeated measurement of the CVL-562 dose response on the neuroimaging index. Therefore, the key power consideration is for a group-level within-subject t-test for the combined partial t-tests (Cohen's d). With anticipated attrition we anticipate a final sample of N=100 complete patient datasets across all sites. However, given that data quality and retention may lead to smaller eventual samples, we projected detectable effect sizes using a projected power of at least 80%, and p<0.05. Given our study design, and the NPC approach, we will be able to detect small-to-medium effect sizes (0.18-0.37) for sample sizes ranging between 25-100 participants with full data. Here, we provide an illustration of the achieved effect sizes at 80% power across possible sample size ranges (Figure 2).

10.1.2 Secondary Endpoint 1

The dose-response-based change in BOLD signal will be examined for each individual participant to see how many participants exhibit a change in BOLD signal. For each individual, a binary outcome will be calculated based on the dose x timepoint x task condition within subject analysis of BOLD signal. We will report the proportion of participants that exhibits a dose response and assess whether this is related to baseline working memory performance.

10.1.3 Secondary Endpoint 2

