We will test if CVL-562 produces a dose-related modulation of sWM performance. We will leverage behavioral data generated during neuroimaging to quantify dose-related CVL-562 effects on sWM performance and also on sWM performance with distraction. Here, the outcome measure will be the sWM performance measured as the angular difference between the target presentation and the participant's response. We will conduct a 4 (task condition--motor, spatial working memory, near-distraction, far-distraction) x 5 (dose) repeated measures ANOVA. Post-hoc analyses will be conducted to demonstrate the directional effects of behavioral performance with respect to dosing. All statistics will be corrected for multiple

comparisons.

10.1.4 Secondary Endpoint 3

We will directly examine the association between sWM performance and task-evoked BOLD signal. An analysis of variance of the dose-dependent effects of CVL-562 on the task-evoked BOLD signal will be conducted as described for the Primary Endpoint, but instead will use the trial-by-trial regressor of sWM performance as a covariate. sWM performance will be measured as described in Secondary Endpoint 2, and will be treated as a covariate of interest in the above-specified general linear model. An effect of a 5 (drug dose) x 4 (task condition) interaction with the sWM precision covariate would indicate that the drug has an effect of BOLD signal change that is specifically associated with a change in trial-by-trial sWM performance.

10.1.5 Secondary Endpoint 4

We will conduct an analysis of variance of the dose-dependent effects of CVL-562 on the functional connectivity of brain regions during spatial working memory. In contrast to the task-evoked modeling, here we will use 'time point' selection methods to isolate specific time points during the delay period of each trial, which we will combine into a time series. This BOLD signal will be used to co-vary a given region of interest with the rest of the brain. Given prior work by our team we will focus on the fronto-parietal control network (FPCN) as a 'seed' region for this task-evoked FC analysis. Specifically, we will quantify covariation of the extracted FPCN signals with all other CIFTI greyordinates. This index of FPCN 'functional integrity' will be obtained across sWM conditions and CVL-562 doses for each subject and will then be entered into 2nd-level random effect analyses.

10.1.6 Secondary Endpoint 5

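### Secondary Endpoint 2 is planned as a 4 x 5 repeated measures ANOVA with no rule for missing dose sessions; a mixed model with the same error strata would keep every usable session at little cost

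*Combined protocol and SAP*

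**What the plan says.** Section 10.1.3 defines the outcome as "the angular difference between the target presentation and the participant's response" and the analysis as follows: "We will conduct a 4 (task condition--motor, spatial working memory, near-distraction, far-distraction) x 5 (dose) repeated measures ANOVA". Post-hoc tests for direction and a multiplicity correction follow. It states no analysis set, no error structure and no handling of a missing or unusable dose session. No other section supplies a rule for this endpoint. Random-effect analyses are named only for Secondary Endpoints 4 and 5.

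The plan expects incomplete participants. Of 120 recruited, section 4.2.1 says "we aim to have 100 participants complete full procedures (we have estimated attrition of 20 participants". The power paragraph of 10.1.1, written for the imaging endpoint, allows for more loss: "given that data quality and retention may lead to smaller eventual samples".

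The outcome depends on the scan session. Section 3.3 says of it: "This will be examined using the behavioral data generated during neuroimaging". Three provisions can cost sessions:
- Section 7.2.2, on scanning: "if at any time a participant requests so, we will stop the imaging session immediately".
- Section 5.2, on acute anxiety in the scanner: "participants will be removed from the scanner and assessed for continuation in the study".
- Section 4.1.1: "Subjects who experience any intolerable effects at any point will not be permitted to continue participation".

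**The concern.** A 4 x 5 repeated measures ANOVA needs all 20 cells from each participant. Standard software deletes anyone with a missing cell, so a participant with four good sessions and one missing contributes nothing.

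This endpoint is the trial's planned test of whether CVL-562 changes spatial working memory performance. Complete-case use would discard sessions that participants have already completed and would widen the interval for every dose contrast. With no written rule, the handling of incomplete participants could also be settled after the data are seen.

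**Working it through.** **The plan's own figure.** 100 / (1 - 20/120) = 120, so the recruitment target reproduces exactly. No power is stated for Secondary Endpoint 2.

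**Inputs from the documents.** 120 recruited and 20 lost (4.2.1); 25 mg at the last test visit in 75%, otherwise at one of the other four, other doses in random order (4.4).

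**Assumptions.** The time at which the 20 leave; equal use of the other four visits for 25 mg; two-sided 0.05 before multiplicity correction; no visit term; d is the mean dose-placebo difference divided by the SD of the paired difference.

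**Method.** Take session means with unit within-participant variance. Let m be a participant's vector of five 0/1 indicators for sessions present, and k their sum. The information matrix sums diag(m) - mm'/k over participants. Effective pairs = 2 / var(dose - placebo). With 100 complete participants the variance is 2/100, which returns 100 pairs. Detectable d at 80% power = (1.96 + 0.84)/√n = 2.80/√n. Power = Φ(d√n - 1.96).

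**Planned attrition only** (simulated trials; the ANOVA has 100 pairs, detectable d 0.280, and 80% power at d = 0.28 in every row):

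| The 20 leave after | Effective pairs, 1/4/15 mg | 25 mg | Power at d = 0.28 |
|---|---|---|---|
| 0-1 sessions | 100 | 100 | 80% / 80% |
| 0-4, uniform | 107 | 104 | 83% / 81% |
| 1-4, uniform | 109 | 105 | 83% / 82% |
| 4, all | 118 | 109-110 | 86% / 83-84% |

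The last row can be checked by hand. Of the 20, 75% (15) lack only 25 mg. The other 5 each lack one of the remaining four treatments, and half of them (2.5) have both a given lower dose and placebo. Direct pairs are 100 + 15 + 2.5 = 117.5, and indirect comparisons add about one. For 25 mg the direct pairs are only 100 + 5 x 3/4 = 103.75, with indirect information supplying the rest. The gain is smaller for 25 mg because most participants receive it last.

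In the 1-4 row the 20 supply on average 20 x 2.5 = 50 sessions. Complete-case analysis discards 50/550 = 9% of usable sessions, and detectable d is 0.280 against 0.268 (lower doses) or 0.274 (25 mg).

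**Single sessions also lost** (illustrative rates, not in the documents, added to the 1-4 row). Complete sets are close to 100(1 - q)^5:

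| q | Complete sets | Effective pairs, lower / 25 mg | Detectable d, ANOVA against mixed model (lower doses) |
|---|---|---|---|
| 2% | 90 | 106 / 102 | 0.295 against 0.272 |
| 5% | 77 | 102 / 98 | 0.319 against 0.277 |
| 10% | 59 | 95 / 92 | 0.365 against 0.287 |

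**Is the replacement safe?** With complete data, 2,000 simulated trials gave the same dose p-value for the planned ANOVA and the mixed model (largest difference 2 x 10⁻⁷). Under planned attrition, with session variance an assumed 10 / 20 / 30% of within-participant variance, type I error for dose was:
- complete-case ANOVA: 4.5 / 4.6 / 5.6%
- mixed model with a participant-by-session term: 5.0 / 4.6 / 5.4%
- mixed model with a participant intercept only: 13 / 21 / 31%

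With an assumed participant-by-condition variance of 0.3, the dose x condition test ran at 4.9% for the ANOVA, 0.4% for a mixed model without that term and 4.5% with it. The random terms must therefore be written out.

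**The case against.** **Listwise deletion is inferred.** A reader might conclude that the plan prescribes a complete-case analysis. It does not. The references to complete datasets and full data in 10.1.1 are sample-size wording for the imaging endpoint. What stands is that no rule is given and that the usual default is deletion.

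**The mixed model itself adds little.** The effective pairs above come from within-participant least squares, so an unbalanced ANOVA with participant as a block would reach the same precision. This is correct: the gain comes from retaining incomplete participants. The mixed model is a convenient way to do so with the right error terms.

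**The gain may be nil.** The 20 are counted from participants eligible for dosing, and Visit 2 may fall up to 8 weeks after Visit 1. Some may leave undosed or after one session and add no within-participant dose information. This stands, and it is why the result is a range.

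**The larger losses are not shown.** A reader might take 77 or 59 complete sets as the plan's expectation. The documents give no session-loss rate, and a participant missing one session may already be among the 20. Sessions can also be postponed: after symptoms (4.3), after a positive urine test (7.2.3), when the drug is held for vital signs (7.2.4), and within windows of 48 hours to 2 weeks (section 8). A scan stopped part-way may still give usable joystick data from completed runs, and a scan that fails only imaging quality control need not lose the behavioural outcome.

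**The planned test is valid.** A reader might infer an inflated error rate. The simulations show none for the ANOVA; the 13 to 31% figures belong to a mis-specified alternative that nobody planned.

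**Conclusion.** The point holds as a cheap gain in precision for a secondary endpoint; it does not correct an error. Section 10.1.3 leaves missing dose sessions without a rule while the plan expects 20 of 120 participants to be incomplete. Under that attrition alone, keeping all usable sessions moves each dose-placebo contrast from 100 pairs to between 100 and about 118 (lower doses) or 110 (25 mg), which is 0 to 6 points of power at d = 0.28. The size rests on the unstated timing of dropout. Larger gains are conditional on permanent single-session loss at undocumented rates; at an illustrative 5%, about 77 complete sets compare with 102 / 98 effective pairs.

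It would be too strong to say that the mixed model removes bias from dose-related dropout. It assumes data missing at random, and neither it nor the complete-case ANOVA protects against loss that depends on unobserved performance.

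**What to change.** In 10.1.3, specify a linear mixed model fitted to every usable session of every dosed participant:
- fixed effects: dose, condition, dose x condition;
- random effects: participant, participant-by-session (the same as participant-by-dose here) and participant-by-condition.

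Define a usable session for the behavioural outcome separately from imaging quality control, including how many trials per condition a partly completed scan must supply. Keep the complete-case 4 x 5 ANOVA as a sensitivity analysis. Tabulate missing sessions by dose and reason, so that any dose-related loss is visible.

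The cost is a few sentences and slightly more code, with no added visits or procedures. The model brings a missing-at-random assumption and, like the uncorrected ANOVA, assumes equal correlation between sessions.

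A visit term is a separate decision. It would separate practice from dose, but because 25 mg is last in 75% of participants it would cut the 25 mg contrast to about 66 effective pairs (1-4 row), below the planned ANOVA's 100. It should be justified on its own or run as a sensitivity analysis.

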11. ADMINISTRATIVE AND REGULATORY

11.1 Multicenter Management and Coordination

The Yale University Coordinating Site Project Management team will support the PI with the multi-site management aspects of this trial. This includes, but is not limited to, study start-up, regulatory assistance (IRB submissions, amendments, and renewals), provision of template study forms (tracking and eligibility checklists, etc.), site qualification and activation, training, and overall project management. The Coordinating Site Project Management team will provide tools to assist the study teams in conducting the trial appropriately and according to ICH Good Clinical Practice.

The Coordinating Site Project Management team will ensure that all participating sites undergo training in which all key study personnel will be instructed study procedures, informed consent, source documentation requirements, safety and adverse event reporting, Good Clinical Practice guidelines and additional study related topics. This training will be conducted by the Yale Center for Clinical Investigation (YCCI) Study Monitor and/or Project Management staff and documentation of completion will be required for all personnel. The PI will be available to site investigators for questions and re-training (if necessary).

After a site initiation visit, which includes Good Clinical Practice (GCP), participating sites will receive a regulatory start up packet from the Project Manager or designee prior to beginning study procedures. The start up packet will contain all required regulatory documentation and procedures that will need to be completed prior to site activation. Upon satisfaction of these requirements, each site will receive a site initiation letter from the Project Manager or designee indicating the site is fully activated and can begin enrollment and study procedures. All regulatory documents will be maintained on site and accessible for monitoring visits.

